5 STUDY RATIONALE

Contact layer (CL) dressings are primary dressings mainly adapted to the management of most non-complicated acute wounds or of chronic wounds at the proliferative stage. While numerous types of CL dressings are available, they all share a common basic structure composed of a thin non- or low-adherent layer which is impregnated with various compounds according to manufacturers. Their main objective is to protect the granulation tissue growth and re-epithelialization from external stresses in order to promote a smooth tissue repair process. They are furthermore expected to limit peri-wound skin irritation and, while not appropriate to manage strong exudation, to favor drainage of excessive wound fluids toward a secondary absorbent dressing which can be simple gauzes. In addition, CL dressings changes should be atraumatic for the viable tissue and as painless as possible.

This latter point was the main limitation of the first available CL dressings which were composed of a simple nylon or polyester layers impregnated with petrolatum or paraffin [1]. If left in place over 3-4 days or more, the compound impregnating the layer was absorbed by the secondary dressing and to a less extent by the wound bed itself [2]. The consequence was a drying of the dressing which then will adhere to the wound and to the skin around. Dressing removal was therefore frequently rather painful and might injured viable underlying tissues. Another disadvantage was that the meshes of the layer could be too large with a growth of granulation tissue through the mesh increasing possible risk of wound injury at removal.

One of the main technical developments that allowed limiting this possible problem, was the use of a mixture of carboxymethylcellulose (CMC) particles combined with lipidic particles. This mixture, when applied onto wound bed, makes a gel which will favour atraumatic removal and, on the other hand, will improve fluid management via the CMC water-absorbing properties. A largely used representative of this approach is represented by the UrgoTul® dressing [3, 4].

The Lomatuell Pro® dressing belongs to this category of CL and is rather similar to UrgoTul®. It might have additional useful properties such as a better conformability to wound and periwind anatomical shapes and it might help in regulating wound moisture (in particular of dry wounds) and prevent risk of maceration.

Due to the lack of controlled trials comparing these dressings, the choice by health professionals is primarily based on empirical evidences and personal experiences [5].

For these reasons, the main purpose of this study was to compare Lomatuell Pro® to UrgoTul® in order to confirm the non-inferiority on pain induced by dressing removal when managing acute wounds, an important clinical problem in daily care [6, 7]. This parameter reflects the potential of a dressing to become adherent to wound bed and is a major issue for French Health Authorities to provide reimbursement for this group of dressings [8].

6 STUDY OBJECTIVES

6.1 Main study objective

To document the non-inferiority of Lomatuell Pro® versus UrgoTul® on pain induced at first dressing removal in the management of acute wounds.

6.2 Secondary study objectives

To compare between the two dressings:

- Complete healing at day 21
- Condition of the wound at study end: overall and according to moisture status at inclusion (e.g. wound shift supporting moist wound healing during treatment)
- Condition of the surrounding skin and efficiency of the CL to drain exudates (exudate management)
- Global satisfaction of user
- Subjects' global assessment
- Safety

7 INVESTIGATION PLAN AND PROCEDURES

7.1 Overall Design and Flow Chart

This will be a national, multicenter, prospective, randomized in parallel groups, non-inferiority, open-label investigation conducted in France.

Approximately 100 study nurses are planned to participate in the investigation in order to enrol 168 subjects (i.e. 84 per group).

The subjects will be seen for maximum 21 (+2) days and will be followed by their investigator at 3 investigational visits (V): V1 at D0, V2 at D3±2 days and V3 at D21+2 days or earlier, as soon as the wound is epithelialized completely. In case the wound will not fully epithelialized within 23 days or the patient will preliminary discontinue the study treatment for any reason, he or she will receive further treatment of the investigators' choosing according to the actual wound condition and the national standards of care.

Between V2 and V3, additional dressing changes can be performed as often as necessary according to the instruction for use of the investigational product assigned. Lomatuell Pro® and UrgoTul® may be left in place up to 7 days.

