7.8.2 Efficacy Measurements and Variables

7.8.2.1 Main Objective

Variable

The main criterion corresponds to the percentage of non-painful dressing removals defined as the percentage of dressing removals associated with a value < 30 mm on a VAS assessing pain scale (0 to 100 millimeters) evaluated at the first dressing removal (V2, D3±2).

This 30 mm threshold is recognized to differentiate a weak pain (score <30 mm) from a moderate (score ≥30 mm) to severe (score >50 mm) one [9-12].

Measurement

Subjects will be asked by investigators to rate their pain intensity perceived at the first dressing removal (V2, D3±2). Pain assessment will be performed using a Visual Analog Scale (VAS). The VAS is a 100 mm straight line ranging from 0 to 100, on which the subject will indicate his/her pain. Subjects will beforehand be informed that the beginning of the scale refers to "no pain" (0) and the end to the most severe intensity of pain they can have (100). Painless dressing change is defined as pain < 30 mm on the VAS. The results obtained during the first dressing removal visit (V2, D3±2) will be filled in by the investigator in the CRF.

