Global assessment of the dressing by the investigator

The dressing use will be evaluated by means of a specific questionnaire to be completed by the investigator at V2 and V3 or ET: ease of handling, ability to maintain its integrity, ease of application, ability to be repositioned, conformability, wound adhesion, ability of dressings to stay in place, transparency, ability to transfer wound fluid to the secondary dressing, ease/speed of removal, absence of residue, overall impression.

Global assessment of the dressing by the subject

The dressing use will be evaluated by means of a specific questionnaire to be completed by the subject at the end of the study (V3 or ET): ease of handling, ability to maintain its integrity, ease of application, ability to be repositioned, ability of dressings to stay in place, transparency, comfort of the patient, ability to transfer wound fluid to the secondary dressing,

ease/speed of removal, overall impression.

Assessments from the study nurse's booklet

For any additional dressing changes what will occur between V2 and V3, the study nurse will be asked to report at each dressing change in his/her booklet carefully and legibly: number of the additional visit, date of the visit, reason for dressing change, presence of complete reepithelialization, appearance of the dressing before removal, bleeding during dressing removal, appearance of the wound bed, appearance of the surrounding skin, amount of exudate, wound moisture, local treatment, number of dressings used, application of dressing, secondary dressing, initials of person in charge of dressing change.

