18.3.1 Visual Analogue Scale

The VAS is used to grade the patient's pain and pain relief. It is a scale from 0 to 100 mm whitout any millimetter marks. The ends correspond to "0 = no pain" and "100mm = unbearable pain".

This specific ruler will be provided to the investigator in order to measure the VAS score. The subject will mark on the ruler the point that he/she feels represent his/her perception of his/her current pain. The VAS score will be directly measured by the investigator. The VAS score will be filled in the CRF.

Visual Analog Scale

When presented to the patient, the scale should be in the **horizontal position**. The patient should be asked to rate his/her pain in relation to a prior usual type of pain, for example, "When you have a headache, where would you say you are on the scale? And what is the pain like now? Stronger or not as strong?").

The **result in millimetres** is to be noted on the CRF form. It should not be **communicated to the patient**.

The method requires good motor coordination on the part of the patient, and it has other limitations, e.g. patients with limited capacity for abstract thought, those with poor eyesight and the elderly.

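### The patient's own pain mark decides the primary endpoint, yet the protocol does not keep the product's identity from the patient: masking name and pack would be a cheap improvement

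*Protocol*

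**What the plan says.** The design is open-label with no exception for the patient: "This will be a national, multicenter, prospective, randomized in parallel groups, non-inferiority, open-label investigation conducted in France" (Protocol 7.1; the synopsis agrees). The primary criterion is the "percentage of dressing removals associated with a value < 30 mm on a VAS assessing pain scale" at V2 (7.8.2.1). On who rates it, the same section says: "Subjects will be asked by investigators to rate their pain intensity perceived at the first dressing removal". Appendix 18.3.1 confirms who places the mark: "The subject will mark on the ruler the point that he/she feels represent his/her perception of his/her current pain". The patient also completes a product questionnaire: "The dressing use will be evaluated by means of a specific questionnaire to be completed by the subject at the end of the study" (7.8.2.2).

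The investigator receives the allocation by email (7.9.3), and the patient is fully informed about the investigation at V1 (7.2.2.1). No section says whether the patient is told, or shown, which product is used.

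Blinding appears only for the reading of wound photographs (7.7 to 7.9.1.2 and 10.1), where the stated aim is to reduce bias. That serves healing, a secondary endpoint.

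The pain rating does have safeguards. Appendix 18.2 prescribes a standardised removal and neutral phrasing, and rules out phrases that announce pain. Appendices 18.2, 18.3.1 and 18.3.2 withhold the score from the patient. The supplied SAP is written for a different product, Suprasorb C, and plans no formal comparison, so it adds nothing here.

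**The concern.** A patient who knows whether the dressing is the sponsor's product or the established comparator may rate the same sensation differently. The nurse who applies the dressing cannot be masked, but the nurse does not place the mark. The protocol blinds the photograph reader for a secondary endpoint and leaves the rater of the subjective primary endpoint unmasked.

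The exposure is real because the endpoint is a single cut-off and few painful removals are expected. The direction is unknown: expectation could hide a worse dressing or make an equivalent one look worse. Both analysis sets use the same marks, so requiring PP and mITT to agree does not correct a biased mark.

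**Working it through.** **Inputs from the protocol.** Expected rate 95%, margin 10 points, one-sided 2.5%, 80% power, 75 evaluable and 84 randomised per arm (7.9.2). Success requires non-inferiority in both PP and mITT, with missing primary data counted as failure in mITT (7.9.1.2). The interval method is not named, so Wald and Newcombe are both shown.

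**The plan's own figure.** n = (1.960 + 0.842)² × (2 × 0.95 × 0.05) / 0.10² = 74.6, so 75 per arm. 75 / 0.90 = 83.3, so 84. Both reproduce. Power at 75 by the normal approximation is Φ(0.10 / √(0.095/75) − 1.960) = 80.2%; exact enumeration of the Wald rule gives 81.7%.

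**How few patients matter.** At 95%, expected painful removals are 0.05 × 84 = 4.2 per arm. One patient is 1/84 = 1.2 points; three are 3.6 points.

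**Illustration A: expectation favours Lomatuell Pro.** Assumptions, none from the documents: true rates 85% and 95%; the reported Lomatuell Pro rate is lifted to 88% or 90%; the UrgoTul rate is unaffected. With 0.15 × 84 = 12.6 painful removals expected in the Lomatuell Pro arm, a 3 to 5 point lift means that 2.5 to 4.2 of them are marked below 30 mm. Missingness is random, equal in both arms and counted as failure in mITT; PP is everyone with a VAS. Probability of passing both sets with 84 per arm, Newcombe to Wald:

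| Reported rate | 10% missing | 5% missing | None missing |
|---|---|---|---|
| 85% (no lift) | 1.0-1.4% | 1.3-1.8% | 2.6-3.3% |
| 88% | 4.0-5.1% | 5.2-6.9% | 10.0-12.5% |
| 90% | 8.8-10.9% | 11.5-14.7% | 21.6-26.1% |

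For comparison, a single interval at n = 75 gives 2.6-3.7%, 9.3-12.9% and 19.5-25.9%. Those are not the trial's error rates, because the protocol requires both sets to pass.

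**Illustration B: expectation disfavours Lomatuell Pro.** Both dressings are truly at 95% and the Lomatuell Pro rate is reported as 93% (0.02 × 75 = 1.5 patients). Single interval, n = 75, Wald: Φ(0.08 / √((0.0475 + 0.0651)/75) − 1.960) = 54.2%, down from 80.2%. Exact enumeration gives 58.2%, down from 81.7% (Newcombe: 47.4%, down from 71.8%).

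**Effect of masking on N.** None: 75 and 84 per arm, 168 in total.

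**The case against.** Four objections carry weight.

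- **The size is assumed.** Nothing in the documents supports a 2 to 5 point shift, or a shift in one arm only. This stands, and the figures above show sensitivity only. A reader might also take 9-26% as the risk of a false non-inferiority claim. That range comes from one interval at n = 75; under the joint rule something like it (10-26%) arises only if nothing is missing.
- **Safeguards exist.** The neutral script, standardised removal and undisclosed score act directly on suggestion and deserve credit. They do not conceal the dressing, so they are partial.
- **The dressings may be recognisable.** A reader might infer from the statement that Lomatuell Pro "belongs to this category of CL and is rather similar to UrgoTul" that patients could not tell the two apart. Section 5 is describing the category of dressing, not its appearance, and 7.4.1 and 7.4.2 describe different materials. Patients also see the dressing, since they rate its transparency. Full double-blinding is not shown to be feasible, and how many patients could identify the brand is unknown. Withholding name and pack does not need identical appearance.
- **Patients may not know their arm now.** The consent pages are not in the supplied text, so what patients are told cannot be checked. The point is that the protocol is silent, not that patients are shown to be told.

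A reader might also infer that the open label is arbitrary. The documents do not support that. No explicit reason is given, but section 13 presents a minimal-risk study that leaves nursing care unchanged apart from the randomised dressing, and section 7.1 plans for about 100 nurses. Open label is declared consistently and is not an error or a contradiction.

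**Conclusion.** The point holds as a cheap improvement, not as a flaw that invalidates the trial. The documents establish three things: the patient rates the primary endpoint, the trial is open-label, and no supplied text keeps the product from the patient. They do not establish that a bias will occur, how large it would be, or which way it would run.

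Under the stated assumptions, a 3 to 5 point lift for a dressing that is truly at the margin raises the chance of passing from about 1-2% to about 4-11% with 10% missing, or 5-15% with 5% missing. A 2-point drop for an equivalent dressing costs over 20 points of single-interval power. Such a shift cannot be separated from a true difference after the data are in, so it has to be limited by design.

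**What to change.** - In 7.1, 7.2.2.1 and Appendix 18.2, describe the trial as open to the nurse, with the patient masked to product where possible.
- Tell the patient that one of two marketed contact layers is being used and will be named at the end, in wording agreed with the ethics committee.
- Instruct the nurse to keep the pack out of sight and not to name the product until the V2 VAS and the V3 or ET subject questionnaire are recorded.
- Add one CRF item at V3/ET asking which dressing the patient thinks was used, with a do-not-know option. This shows how well the masking held.
- If the patient information already withholds the product, say so in the protocol.

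The cost is wording in the patient information and nurse instructions plus one CRF item, with no change in sample size. The nurse still knows the product. The limitation is that masking will be partial: the dressings differ in material, and some patients may recognise theirs or be told.

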7.2 Procedures and Assessments

7.2.1 Schedule of Assessments

All assessments of the investigation will be conducted as indicated in the following table which displays the frequency and timing of all measurements.

Table 1. Data collection schedule

	Inclusion Intermediate Ad		Additional	Final visit	Early Termination
	visit	visit	visits*	Final visit	visit**
Visit name (corresponding day)	V1 (D0)	V2 (D3±2)	Between V2 and V3	V3 (D21+2 or earlier, as soon as the wound is epithelialized completely)	ET
Oral consent of the patient to	X				
participate					
Inclusion/exclusion criteria	\boxtimes				
Randomization	X				
Demographics	X				
Medical history	X				
Wound/surrounding skin characteristics	×	×	×	X	X
Investigational product application	×	×	×		
Secondary dressing / fixation use	×	×	×		
Dressing removal (to follow the standardized removal procedure)		X	×	X	X
Intake of analgesics	X	×		×	×
Pain assessment (VAS) after application of investigational product	×				
Pain assessment (VAS) during removal		\boxtimes			

Version 2.0 – March 29, 2019

Amount of exudate	X	X	×	X	X
Wound shift (ratio necrotic/ fibrinous/ granulation/ epithelisation tissue)	×	×		X	X
Complete healing assessment		×	×	×	×
Wound photograph	×	×		×	×
Photograph of the investigational product on the wound***	×	×		X	×
Adverse events/Adverse device effects	×	×		×	×
Global dressing investigator evaluation		×		×	×
Global dressing subject's evaluation				X	×
Concomitant treatment	×	X		×	X

^{*} optional, if required by wound's condition

7.2.2 Investigation Procedures

7.2.2.1 Inclusion visit (V1, D0)

At the inclusion visit (V1, D0) the subject will receive complete information related to the investigation. Prior to any assessment, the oral consent of the patient to participate, according to the "Etudes interventionnelles à risques minimes" French regulations, will have to be obtained by the investigator. Inclusion and exclusion criteria will be checked by the investigator.

The subject will be consecutively allocated to a subject code providing they fulfil all inclusion and none of the exclusion criteria. The subject will be randomized to either receive Lomatuell Pro® or UrgoTul®.

The investigator will report the date of visit, and collect subject information in the case report form (CRF) such as demographic characteristics (gender, age, height, weight), significant medical history including the presence and type of disease which could interfere with the evolution of healing, concomitant therapy, intake of analgesics, characteristics of wound (type and duration of the wound, location, size, assessment of the wound bed (bleeding, maceration, inflammation, infection, ratio necrotic/ fibrinous/ granulation/ epithelisation tissue, and tissue in-growth in the dressing holes) and condition of the surrounding skin (inflammatory signs, irritation, allergic rash/eczema, blistering, skin stripping, maceration, dry, trauma to wound edges, product degradation on the skin, hematoma). Assessment of the amount of exudate (drainage) will be performed after removal of the dressing and before wound cleansing and it will be categorized as none, light, moderate, or heavy.

If applicable, the previous treatment or dressing used will be reported in the CRF. The investigator will also interview the subject about the use of analgesics since the wound occurrence including the frequency of use. These data will be reported in the appropriate form of the CRF.

The wound (with a millimetre ruler) will be photographed by the investigator before the first investigational product application according to the photography guidelines (see Appendix

^{**} will be performed for the patients who discontinued the study preliminary for any reason, instead of the visit V3

^{***}after application of the product at V1, before removal of the product and after application of a new product at V2, before removal of the product at V3 or Early termination visit

17.1). A digital camera could be provided to the investigator participating in the investigation in case his/her camera does not meet the level of quality required to analyse wound on photographs or if they do not have any camera.

The investigator will apply the allocated investigational product on the wound. If required, 2 investigational products can be used to cover the wound.

A photograph of the wound with the investigational product in place (before the secondary dressing application) will be taken after dressing application according to the photography guidelines.

A secondary dressing could be applied over the investigational product. The type used will be indicated in the CRF by the investigator. The dressing confection will have to follow the condition mentioned in the protocol in section 7.5.

The pain after dressing application will be assessed by using the visual analogue scale (VAS). The investigator will ask the subject to assess his/her pain level during the care of his/her wound. The subject will be asked to rate the pain he/she felt using a VAS tool.

A specific ruler will be provided to the investigator in order to measure the VAS score. The subject will mark on the ruler the point that he/she feels represent his/her perception of his/her current pain. The VAS score will be directly measured by the investigator with a scale in millimetres. The VAS score will be filled in the CRF.

Adverse events (AEs) / Serious adverse events (SAEs) / Adverse device effects (ADEs) and Device deficiencies (DDs) occurring at/since the first application of the investigational product will be collected by the investigator. The investigator will also ensure that the subject continue the investigation.

The next visit (V2) will be scheduled with the subject three days after the inclusion visit at D3 (± 2 days).

7.2.2.2 Intermediate visit (V2, D3±2)

The intermediate visit must be planned three days after the first investigational product application. If appropriate, a window of two days before or after this expected visit is allowed to make sure that the patient will have the first dressing change as early as necessary according to their condition (i.e. already on the next day after V1).

Adverse events (AEs) / Serious adverse events (SAEs) / Adverse device effects (ADEs) and Device deficiencies (DDs) occurring since the previous visit will be collected by the investigator. Any changes to the concomitant therapy will also be collected. The investigator will also ensure that the subject continue the investigation.

The presence of complete healing status (100% of epithelialization, first epithelia layer) of the wound) will be assessed.

NB! In case of complete epithelialization all procedures, required for Visit 3 should be

performed, data is to be recorded in the CRF section Visit 3. Visit 2 should be marked as "Not performed due to early epithelialization" in the CRF.

Depending on the subject condition, analgesics may be concomitantly prescribed by the investigator. In this case, details on the type of prescribed treatments belonging to analgesic therapeutic class as well as hour of intake before removal (within 2 hours notably) will be recorded in the CRF.

A photograph of the wound with the investigational product in place will be taken before product removal (but after secondary dressing removal, if there was any), according to the photography guidelines (see Appendix 17.1).

The investigator will remove the investigational product by following the standardized removal procedure (see Appendix 17.2). Data about dressing soak will be collected in the CRF.

Pain at the first dressing removal will be assessed by using the visual analogue scale (VAS). The investigator will ask the subject to assess his/her pain level at the dressing removal. The subject will be asked to rate the pain he/she felt at the moment of dressing change using the VAS tool.

After product removal, a photograph of the wound will be taken according to the photography guidelines.

The investigator will assess the wound and surrounding skin condition:

- Wound size estimation
- Assessment of the wound bed (bleeding, maceration, inflammation, infection, ratio necrotic/ fibrinous/ granulation/ epithelisation tissue, and tissue in-growth in the dressing holes)
- Assessment of the surrounding skin (inflammatory signs, irritation, allergic rash/eczema, blistering, skin stripping, maceration, dry, trauma to wound edges, product degradation on the skin, hematoma)
- Global assessment of exudate management (efficiency of the CL to drain exudates to the secondary dressing)

The investigator will evaluate the use of the dressing regarding the following parameters:

- Ease of handling
- Ability to maintain its integrity
- Ease of application
- Ability to be repositioned during application
- Conformability
- Wound adhesion

- Ability of dressings to stay in place
- Transparency
- Ease / speed of removal,
- Overall impression,
- Absence of residue

The investigator will apply the allocated investigational product on the wound. If required, 2 investigational products can be used to cover the wound.

A photograph of the wound with the investigational product in place (before the secondary dressing application) will be taken after dressing application according to the photography guidelines.

A secondary dressing could be applied over the investigational product. The type used will be indicated in the CRF by the investigator. The dressing confection will have to follow the condition mentioned in the protocol in section 7.5.

7.2.2.3 Last visit (V3, D21+2 or earlier, as soon as the wound is epithelialized completely)

The last visit must be planned in 21 (+2) days after the first investigational product application (V1, D0), unless the wound is epithelized (one epithelial layer) earlier. In this case the visit should be scheduled shortly after the epithelialization (but not later as in 23 days after the first investigational product application).

Adverse events (AEs) / Serious adverse events (SAEs) / Adverse device effects (ADEs) and Device deficiencies (DDs) occurring since the previous visit will be collected by the investigator. Any changes to the concomitant therapy will also be collected.

Depending on the subject condition, analgesics may be concomitantly prescribed by the investigator. In this case, details on the type of prescribed treatments belonging to analgesic therapeutic class as well as hour of intake before removal (within 2 hours notably) will be recorded in the CRF.

A photograph of the wound with the investigational product in place will be taken before the investigational product removal (but after secondary dressing removal, if there was any), according to the photography guidelines (see Appendix 17.1).

The investigator will remove the investigational product by following the standardized removal procedure (see Appendix 17.2). Data about dressing soak will be collected in the CRF.

After product removal, a photograph of the wound will be taken according to the photography guidelines.

The investigator will assess the wound and surrounding skin condition:

- Wound size estimation
- Assessment of the wound bed (bleeding, maceration, inflammation, infection, ratio necrotic/ fibrinous/ granulation/epithelisation tissue, and tissue in-growth in the dressing holes)
- Assessment of the surrounding skin (inflammatory signs, irritation, allergic rash/eczema, blistering, skin stripping, maceration, dry, trauma to wound edges, product degradation on the skin, hematoma)
- Global assessment of exudate management (efficiency of the CL to drain exudates to the secondary dressing)

The presence of complete healing status (100% of epithelialization, first epithelia layer) of the wound) will be assessed.

The investigator will evaluate the use of the dressing regarding the following parameters:

- Ease of handling
- Ability to maintain its integrity
- Ease of application
- Ability to be repositioned during application
- Conformability
- Wound adhesion
- Ability of dressings to stay in place
- Transparency
- Ease / speed of removal,
- Overall impression,
- Absence of residue

The global assessment of the product by the patient will also be performed.

